8.3.1.5 Determination of Loss of Response in LTE

During the LTE, participants exhibiting loss of response will have the option to enroll in the OLE. The Investigator will assess loss of response according to the following criteria:

- Increase in UC disease activity as defined by an increase in PMS ≥ 2 points compared to PMS at Week 13 with an absolute PMS ≥ 4 , based on 3 most recent consecutive days of diary entries within 7 consecutive days (averaged and rounded to the nearest integer), AND
- Exclusion of other causes of an increase in disease activity unrelated to underlying UC (eg, *C. difficile* infection, change in medication).

8.3.1.6 Determination of Symptomatic Response in OLE

Participants who failed to achieve clinical response at the end of the Induction Period (Week 13) and entered the OLE will be assessed again by the Investigator at OLE Week 13 for symptomatic response according to the following criteria: decrease from baseline $\geq 30\%$ of the combined RB

and SF scores, based on the 3 most recent consecutive days of diary entries within the 7 days prior to the visit, averaged and rounded to the nearest integer.

8.3.2 Endoscopic Biopsies

Per the inclusion criteria ([Section 5.1](#)), a histopathology report supporting the diagnosis of UC must be available in the source documents prior to randomization. If a histopathology report is not available, the Screening endoscopy may serve as such with histology evaluated at the local histology laboratory.

Biopsies will be obtained at each endoscopy to support assessment of the histopathology endpoints [REDACTED] Up to 4 biopsy pairs (ie, total of 8) will be collected from the most affected area 15 to 25 cm from the anal verge. For participants with proctitis only at baseline, biopsies should be taken 8 to 10 cm from the anal verge.

The original location (colonic segment) of biopsy specimens acquired at Screening must be clearly indicated. Detailed instructions for endoscopic biopsies (eg, number of biopsies, anatomic site, normal or inflamed mucosa) can be found in the Laboratory Manual.

Biopsy samples will be processed by a central laboratory, and histopathologic scoring using the Geboes, Robarts, and Nancy histopathology indices will be performed by a blinded central reader ([Appendix 7](#)).

Biopsy specimen transfer, processing, slide preparation, and digitization of slides for histopathologic scoring procedures will be detailed in a Histopathology Manual. [REDACTED] This will be further delineated in the Laboratory Manual. Histopathology results will not be made available to study sites.

8.3.3 Efficacy-Related Biomarkers

All efficacy-related and exploratory efficacy-related biomarkers will be analyzed by a central laboratory.

Samples for biomarker assessments will be collected according to the SoA ([Section 1.2](#)). Blood, tissue, and stool samples will be analyzed by the central or specialty laboratory. Details for collection, processing, and storage will be provided in the Laboratory Manual. Residual samples will be stored and may be used for additional analyses, if the participant has granted consent and where allowed by the regulatory authorities and local ethics committees.

C-reactive protein: Blood will be collected for measurement of CRP. C-reactive protein is an acute phase protein expressed by hepatocytes in response to inflammatory cytokines and will be assessed using a CRP assay. Investigators will be blinded to the CRP results during the 13-week

Induction Treatment Period, the LTE Treatment Period, and first 4 weeks of the OLE Treatment Period.

Fecal calprotectin: Stool samples will be collected for measurement of FCP. Fecal calprotectin is a complex consisting of calcium-binding proteins. It is expressed by activated neutrophils (and to a lesser extent by macrophages and monocytes), and fecal levels correlate with the number of neutrophils in the gut. It is used as a biomarker of intestinal inflammation. Investigators will be blinded to the FCP results during the 13-week Induction Treatment Period, the LTE Treatment Period, and first 4 weeks of the OLE Treatment Period.

Lymphocyte count: Blood will be collected for measurement of lymphocyte count. VTX002, through modulation of S1P receptors, is postulated to modulate lymphocyte trafficking, resulting in a reduction in peripheral lymphocyte count and lymphocyte availability for recruitment to sites of inflammation. During the 13-week Induction Treatment Period, the LTE Treatment Period, and first 4 weeks of the OLE Treatment Period, Investigators will be blinded to the WBC and differential counts results. The Investigator must take care to avoid ordering or viewing any local CBC during this time. During this time, the WBC differential results will be assessed by an unblinded Medical Monitor (not providing direct medical oversight of study conduct). If either one of the following events occurs, the unblinded Medical Monitor will notify the Investigator with additional instructions:

- ANC (absolute neutrophil count) < 1000/ μ L
- ALC < 200 cells/ μ L

If the ANC is confirmed to be below the 1000/ μ L limit, the Investigator will be requested to closely monitor for risk of serious infection and institute appropriate follow-up at his or her discretion.

If the ALC is confirmed to be below the 200 cells/ μ L limit, study treatment should be interrupted and should not be reinitiated if the ALC remains below this threshold. In this situation, the unblinded Medical Monitor will notify the Investigator and provide instructions on additional actions that the Investigator may need to take. When there is at least one measurement of ALC < 200 cells/ μ L, blinded values may be released to treating physicians and Investigators as deemed medically necessary to monitor infection and/or aid in diagnostic work-up as clinically indicated, and/or as a tool to assess the effectiveness of therapeutic interventions for an infection.

Investigators will repeat CBC with differentials weekly until ALC > 500 cells/ μ L. Reinitiation of study treatment can be considered only when ALC > 500 cells/ μ L.

8.3.4 Exploratory Efficacy-Related Biomarkers

Samples for exploratory biomarker assessments will be collected according to the SoA (Section 1.2). [REDACTED] will be analyzed by a central or specialty laboratory. Details for collection, processing, and storage will be provided in the Laboratory Manual. Residual

samples will be stored and may be used for additional analyses to further understand response to treatment and mechanism of action of VTX002 if the participant has granted consent. These additional analyses (as appropriate) will be conducted only where allowed by the regulatory authorities and local ethics committees.

Samples may be stored for a maximum of 15 years (or according to local regulations) following the last participant's last visit for the study at a facility selected by the Sponsor to enable further analysis of biomarker responses to VTX002, such as proteomics and transcriptomics, if needed.

[REDACTED]

[REDACTED]

[REDACTED]

[REDACTED]

[REDACTED]

8.3.5 Quality of Life

Patient-reported quality of life assessment will be completed electronically and checked for completeness at the study site as indicated in the SoA ([Section 1.2](#)) and will be used in support of the efficacy outcomes.

Inflammatory Bowel Disease Questionnaire: The IBDQ is a validated 32-item questionnaire used to assess HRQoL in participants with inflammatory bowel disease, including UC and Crohn's disease. Response to each of the questions is graded from 1 to 7 with overall score ranging from

32 (very poor HRQoL) to 224 (perfect HRQoL). The IBDQ will be collected if and when available in the appropriate local language.

8.4 Safety Assessments

Planned timepoints for all safety assessments are provided in the SoA ([Section 1.2](#)).

8.4.1 Physical Examinations

A complete PE will include evaluation of heart, lung, head and neck, abdomen, neurological system, skin, and extremities. An interim (or brief) PE will include areas with previously noted abnormalities and/or that are associated with any new complaints from the participant. Please see SoA ([Section 1.2](#)) for more information.

Investigators should pay special attention to clinical signs related to previous serious illnesses.

8.4.2 Vital Signs

Temperature, pulse, BP, and respiratory rate will be assessed. Vital signs will be measured prior to any blood draws that occur at the same study visit.

Blood pressure and pulse will be assessed in the sitting position with a calibrated automated device. Manual techniques will be used only if an automated device is not available. Proper technique should be utilized during the measurement of BP to include the following:

- The participant's arm should be bare and supported at heart level
- An appropriately sized cuff (cuff bladder encircling at least 80% of the arm) should be utilized. Participant's legs should not be crossed during the evaluation

When obtaining the pulse and BP, the participant should rest in the sitting position for at least 5 minutes before measurement to establish an accurate baseline measurement. After the participant has been sitting for at least 5 minutes, pulse and BP will be measured using an automated validated device (if available). Blood pressure and pulse are to be collected prior to completion of the ECG assessment and before any simultaneously scheduled blood collections. See [Section 6.5](#) for guidance for cardiac monitoring.

8.4.3 Electrocardiograms

A12-lead ECG will be obtained as outlined in the SoA (see [Section 1.2](#)) using an ECG machine that automatically calculates the HR and measures PR, QRS, QT, and QTc intervals.

Electrocardiograms should be preceded by at least 5 minutes of rest in the supine position without distractions (eg, television, cell phones) at each timepoint at which an ECG is required.

All ECGs will be recorded from a 12-lead ECG machine with the participant in the supine position. Every attempt should be made to ensure the participant's 12-lead ECG readings are obtained using the same machine throughout the study.

Intervals to be provided on the confirmed read for each safety 12-lead ECG are: RR, PR, QRS, QT and QTcF. If an ECG shows a new onset QTcF interval > 450 msec in men and > 470 msec in women during the treatment period, a repeated ECG is required. If this abnormal finding is confirmed, study treatment must be interrupted. Effective diagnostic and therapeutic strategies should be employed.

Reversible causes of prolonged QTc interval (eg, electrolyte abnormalities or hypomagnesemia) should be corrected as clinically indicated. When evaluating a participant with new onset QTc interval above 500 msec, referral to a cardiologist experienced in treating cardiac conduction disorders should be considered. Reinitiation of study treatment can be considered only after all of the following have occurred:

- The QTcF interval is < 450 msec (men) or < 470 msec (women)
- The QTc prolongation is considered by the Investigator and confirmed by the cardiologist as not related to study treatment and likely caused by other factors
- Individual risk-benefit is favorable (as determined by the Investigator, in agreement with the cardiologist), AND
- After discussion with the Medical Monitor

The Investigator will be responsible for review and interpretation of 12-lead ECGs on site and determining if the 12-lead ECG is normal, abnormal clinically insignificant, or abnormal clinically significant. Findings will be documented in the eCRF. All 12-lead ECG recordings will be transferred to a central reader for analysis. See [Section 6.5](#) for guidance for cardiac monitoring.

8.4.4 Holter ECG Monitoring

Detailed instructions describing the process for recording and transmission of the digital ECGs and Holter can be found in the Study Manual and provided to the site before the start of the study.

Participants should be in the supine position prior to Holter application.

On Day 1 and OLE Day 1 (OLE Week 0/OLE Visit 1), continuous Holter ECG monitoring will be performed for at least 1 hour predose and at least 24 hours postdose using the same device and procedure, as outlined in the SoA (see [Section 1.2](#)). Participants who meet the discharge criteria ([Section 6.5.1.1](#)) will be sent home for continued Holter monitoring at least 24 hours postdose. Participants will be instructed regarding removal and return of the Holter monitor. All Holter recordings will be transferred to a central reader for analysis.

See [Section 6.5](#) for guidance for cardiac monitoring.

8.4.5 Pulmonary Function Tests

Pulmonary function tests will be performed according to the SoA ([Section 1.2](#)) and include FEV1 and FVC measurements. At sites where available, diffusing capacity of the lungs for carbon monoxide (DLCO) measurements will also be performed. These tests will be performed at a qualified pulmonary function laboratory or respiratory department.

If the PFTs are not within normal range, the results should be verified by a pulmonologist, and potential confounding factors identified. If the participant has a decline in PFT values, the participant should be evaluated by a pulmonologist. If values (FEV1 and/or FVC) decline below 50% of the predicted values, treatment should be discontinued with follow-up evaluation initiated as appropriate. An inability to perform a test for DLCO should be discussed with the Sponsor.

The safety of study participants and site staff is paramount, so it is at the Investigator's discretion whether PFT can be safely administered to study participants during the treatment period. The Investigator should evaluate on a case-by-case basis how best to proceed based on the participant's medical history, the Investigator's clinical judgment, and in consultation with the Medical Monitor. All reasonable efforts should be made to ensure safety and adherence to the protocol. When available, spirometry may be conducted at the clinical site instead of at the pulmonary laboratory. If the decision is made that it is not appropriate to conduct PFTs due to the safety concerns (eg, SARS-CoV-2 transmission), then this decision and rationale should be appropriately captured in the participant's source documentation. When available and safe (due to lifting of local restrictions, reopening of local PFT labs, or improved safety conditions), the tests should be conducted as soon as possible and as close to the timepoints as outlined in the protocol.

8.4.6 Ophthalmoscopy and Optical Coherence Tomography

Ophthalmoscopy and OCT will be performed according to the SoA ([Section 1.2](#)). A general ophthalmologist can do the OCT examination, although a retinal specialist would be preferred to do the examinations, wherever possible.

For participants with abnormal OCT findings, with visual signs or symptoms of new onset macular edema, or a suspicion of new onset macular edema or worsening macular edema following initiation of treatment, general retinal examinations, including eye history, visual acuity, and dilated ophthalmoscopy should be obtained along with OCT. Additional testing should be considered at the discretion of the ophthalmologist.

8.4.7 Tuberculosis Screening and Chest X-Ray

All participants will complete TB screening to determine eligibility (see Exclusion Criterion 15).

A positive diagnostic TB test is defined as:

- A positive QuantiFERON test or 2 successive indeterminate QuantiFERON tests **OR**

- A tuberculin skin test reaction ≥ 10 mm (≥ 5 mm in participants receiving the equivalent of > 15 mg/day prednisone), if a QuantiFERON test is not available

Chest X-ray is to be performed at the time of Screening if not done in the previous 6 months.

Participants with active or latent TB infection at Screening, and history of untreated or inadequately treated latent TB infection will be excluded from the study. The following are EXCEPTIONS to this exclusion criterion:

- a. Participants with latent TB, who have been ruled out for active TB, have completed an appropriate course of TB prophylaxis treatment per national/local medical guidelines or WHO guidelines, have a chest radiograph without changes suggestive of active TB infection, and have not had recent close contact with a person with active TB are eligible to enroll in the study. It is the responsibility of the Investigator to verify the adequacy of previous TB treatment and provide appropriate documentation of treatment compliance.
- b. Participants diagnosed with latent TB at Screening, ruled out for active TB and have received at least 4 weeks of an appropriate TB prophylaxis regimen may be rescreened for enrollment. Participants will complete their prophylactic regimen during the trial.

8.4.8 Clinical Safety Laboratory Assessments

See [Appendix 3](#) for the list of clinical laboratory tests to be performed and the SoA ([Section 1.2](#)) for the timing and frequency.

The Investigator must review the laboratory report, document this review, and record any clinically relevant changes occurring during the study in the AE section of the eCRF. The laboratory reports must be filed with the source documents. Clinically significant abnormal laboratory findings are those that are not associated with the underlying disease, unless judged by the Investigator to be more severe than expected for the participant's condition.

All laboratory tests with values considered clinically significantly abnormal during participation in the study or within 14 days after the last dose of study treatment should be repeated until the values return to normal or baseline or are no longer considered clinically significant by the Investigator or Medical Monitor.

If such values do not return to normal/baseline within a period of time judged reasonable by the Investigator, the etiology should be identified, and the Sponsor or their designee notified. All protocol-required laboratory assessments, as defined in [Appendix 3](#), must be conducted in accordance with the Laboratory Manual and the SoA ([Section 1.2](#)). If laboratory values from nonprotocol-specified laboratory assessments performed at the institution's local laboratory require a change in participant management or are considered clinically significant by the Investigator (eg, SAE or AE), then the results must be recorded in the eCRF.

8.5 Adverse Events

The definitions of an AE and SAE can be found in [Appendix 4](#).

Adverse events will be reported by the participant (or, when appropriate, by a caregiver, surrogate, or the participant's legally authorized representative).

The Investigator and their designees or site staff are responsible for detecting, documenting, and recording events that meet the definition of an AE or SAE and remain responsible for following up AEs that are serious, considered related to the study treatment or study procedures, or that caused the participant to discontinue the study treatment (see [Section 7.0](#)).

8.5.1 Time Period and Frequency for Collecting AE and SAE Information

All AEs and SAEs will be collected from the signing of the ICF to 30 days after last study treatment administration. Medical occurrences that begin before the start of study treatment but after obtaining informed consent will be recorded on the Medical History/Current Medical Conditions section of the eCRF, not the AE section.

All SAEs will be recorded and reported to the Sponsor or designee within 24 hours of learning of a participant's SAE, as indicated in [Appendix 4](#). The Investigator will submit any updated SAE data to the Sponsor or designee within 24 hours of becoming aware.

Investigators are not obligated to actively seek AE or SAE data after conclusion of the study participation. However, if the Investigator learns of any SAE, including death, at any time after a participant has been discharged from the study, and he/she considers the event to be reasonably related to the study treatment or study participation, the Investigator must promptly notify the Sponsor.

The method of recording, evaluating, and assessing causality of AE and SAE and the procedures for completing and transmitting SAE reports are provided in [Appendix 4](#).

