5.4 Screen Failures

Screen failures are defined as participants who consent to participate in the clinical study but are not subsequently randomly assigned to study treatment/entered in the study. A minimal set of screen failure information is required to ensure transparent reporting of screen failure participants to meet the Consolidated Standards of Reporting Trials publishing requirements and to respond to queries from regulatory authorities. Minimal information includes demography, screen failure details, eligibility criteria, and any SAEs.

Individuals who do not meet the criteria for participation in this study (screen failures) may be rescreened. If a participant is being considered to be rescreened more than once, please contact the

Medical Monitor. Rescreened participants should not be assigned the same participant number as for the initial screening.

If a participant is considered for rescreening, the need for repeat testing should be discussed with the Medical Monitor. Upon approval by the Medical Monitor, if a participant is rescreened within 6 months a repeat chest X-ray is not required. If a participant is rescreened within 3 months, OCT does not need to be repeated if the participant does not have any visual symptoms, and PFTs do not need to be repeated if the participant does not have any respiratory symptoms.

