- b) Details of liver chemistry stopping criteria and required actions and follow-up assessments after liver stopping or monitoring event are given in [Section 6.6](#). An increase in AST or ALT $> 3 \times$ ULN should be followed by repeat testing within 72 hours of receiving results to confirm the abnormality and determine whether AST or ALT is increasing or decreasing. All events of ALT or AST $> 3 \times$ ULN and total bilirubin $> 2 \times$ ULN ($> 35\%$ direct bilirubin), or ALT or AST $> 3 \times$ ULN and INR > 1.5 , if INR measured, which may indicate severe liver injury (possible Hy's Law), must be reported as an SAE.
- c) eGFR will be calculated each time the serum creatinine is tested.

[REDACTED]

Appendix 4 Adverse Events: Definitions and Procedures for Recording, Evaluating, Follow-Up, and Reporting

See [Section 8.5](#) for additional information regarding AEs and SAEs.

Definition of AE

AE Definition
 
 • An AE is any untoward medical occurrence in a participant, temporally associated with the use of study treatment, whether or not considered related to the study treatment. • NOTE: An AE can therefore be any unfavorable and unintended sign (including an abnormal laboratory finding), symptom, or disease (new or exacerbated) temporally associated with the use of study treatment.

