
Events NOT Meeting the AE Definition
 
 • Any clinically significant abnormal laboratory findings or other abnormal safety assessments which are associated with the underlying disease, unless judged by the Investigator to be more severe than expected for the participant’s condition. Medical occurrences that begin before the start of study treatment but after obtaining informed consent will be recorded on the Medical History/Current Medical Conditions section of the eCRF, not the AE section. • The disease/disorder being studied or expected progression, signs, or symptoms of the disease/disorder being studied, unless more severe than expected for the participant’s condition • Medical or surgical procedure (eg, endoscopy, appendectomy): the condition that leads to the procedure is the AE • Situations in which an untoward medical occurrence did not occur (social and/or convenience admission to a hospital) • Anticipated day-to-day fluctuations of preexisting disease(s) or condition(s) present or detected at the start of the study that do not worsen

Definition of SAE

If an event is not an AE per definition above, then it cannot be an SAE even if serious conditions are met (eg, hospitalization for signs/symptoms of the disease under study, death due to progression of disease).

An SAE is defined as any untoward medical occurrence that, at any dose:
a) Results in death
b) Is life-threatening The term “life-threatening” in the definition of “serious” refers to an event in which the participant was at risk of death at the time of the event. It does not refer to an event which hypothetically might have caused death if it were more severe.
c) Requires inpatient hospitalization or prolongation of existing hospitalization In general, hospitalization signifies that the participant has been detained (usually involving at least an overnight stay) at the hospital or emergency ward for observation and/or treatment that would not have been appropriate in the physician’s office or outpatient setting. Complications that occur during hospitalization are AEs. If a complication prolongs hospitalization or fulfills any other serious criteria, the event is serious. When in doubt as to whether “hospitalization” occurred or was necessary, the AE should be considered serious. Hospitalization for elective treatment of a preexisting condition that did not worsen from baseline is not considered an AE.

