17. SAFETY

17.1 Adverse Events

17.1.1 General Considerations

Adverse events are collected from the date and time of signing ICF and will be coded according to the MedDRA version 26.0 or higher. Adverse events with an onset prior to first dose of study treatment are collected as part of medical history. Adverse events with an onset on or after first dose of study treatment are collected on adverse event eCRFs. All AE tables will be summarized according to the actual treatment group with an appropriate safety set.

A treatment-emergent adverse event (TEAE) is either an AE occurring on or after the date and time of first study treatment intake, or an ongoing AE worsening in severity after the date and time of the first study treatment. If an AE date coincides with the date of first dose of study treatment and either the AE onset time or drug administration time is missing then the AE will be considered treatment-emergent. AEs having both start and end dates missing will also be considered treatment-emergent. AEs with a missing onset date and non-missing end date will be considered as TEAE unless end date is prior to the first drug administration. Adverse events with missing seriousness will be considered serious. Adverse events with missing severity will be considered to have CTCAE grade 3. Adverse events with missing relatedness will be considered related.

AEs with an onset prior to the date and time of first study treatment intake (i.e., during Screening) will be listed but will not be summarized unless they either result in a TEAE due to AE worsening in severity or are serious. TEAE summaries will be separately prepared for study periods of Induction Treatment Period, LTE, OLE, and for the entire study:

- TEAEs with an onset on or after date and time of first study treatment intake during the Induction Treatment Period but prior to last participation in the Induction Treatment Period will be associated with Induction. Also, TEAEs resulting from worsening of severity during Induction in an AE having onset during Screening will be associated with Induction. Summaries for the Induction Treatment Period will use the Safety Set. This set of TEAEs will be associated with the Induction Period Analysis.

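### Protocol 8.5.1 and Appendix 4 give opposing instructions on whether a serious event between consent and first dose is an SAE

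*Protocol*

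**What the plan says.** Protocol 8.5.1 opens with "All AEs and SAEs will be collected from the signing of the ICF to 30 days after last study treatment administration". The next sentence is "Medical occurrences that begin before the start of study treatment but after obtaining informed consent will be recorded on the Medical History/Current Medical Conditions"; it goes on to exclude the AE pages expressly. The following paragraph states "All SAEs will be recorded and reported to the Sponsor or designee within 24 hours of learning of a participant's SAE" and points to Appendix 4 for how this is done.

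Appendix 4 defines the terms. "An AE is any untoward medical occurrence in a participant, temporally associated with the use of study treatment". The Medical History sentence appears again there, in the box of events that do not meet the AE definition. The SAE definition then begins: "If an event is not an AE per definition above, then it cannot be an SAE even if serious conditions are met".

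Protocol 5.4 lists what must be kept on screen failures, who by definition are not randomized: "Minimal information includes demography, screen failure details, eligibility criteria, and any SAEs". Table 1 of the Schedule of Activities marks adverse events in the Screening column. Protocol 6.10 asks for medication given for a study-related AE to be recorded from the time of consent.

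SAP 17.1.1 says AEs are collected from consent, but also "Adverse events with an onset prior to first dose of study treatment are collected as part of medical history", with the AE eCRFs holding events from first dose onward. SAP 13 has the same routing. SAP 17.1.1 nevertheless plans to summarize pre-dose AEs that are serious, and it states "TEAEs resulting from worsening of severity during Induction in an AE having onset during Screening will be associated with Induction".

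**The concern.** Sites have to act on this instruction within 24 hours, and the protocol answers the question both ways. The period is not free of study-related risk. Under 8.3.1.2 an endoscopy is required before randomization, and under 8.3.2 biopsies are taken at each endoscopy, up to eight specimens. Harm from those procedures is harm from taking part in the study, even though no drug has been given. If one site reports such an event as an SAE and another files it as history, sponsor oversight in that window depends on which page of the protocol the site happened to follow.

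The SAP has a matching problem. It plans to summarize serious pre-dose AEs, but it sends those events to a data source that neither document says carries a seriousness assessment.

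**Working it through.** No arithmetic applies. The check sets the passages side by side and then follows one event through them.

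**Text that implies capture as AE or SAE from consent**
- 8.5.1, first sentence: the collection window opens at ICF signature.
- 8.5.1, SAE paragraph: all SAEs within 24 hours, with no restriction to the period after first dose.
- 5.4: SAEs are part of the minimum data on screen failures.
- Schedule of Activities, Table 1: adverse events are marked at Screening.
- 6.10: medication for a study-related AE is recorded from consent.
- SAP 17.1.1: AE collection starts at consent, and serious pre-dose AEs are summarized.

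**Text that directs the other way**
- 8.5.1, second sentence: occurrences after consent and before treatment go to Medical History.
- Appendix 4, AE definition: tied in time to use of study treatment.
- Appendix 4, events not meeting the AE definition: the Medical History sentence is repeated there.
- Appendix 4, SAE definition: a non-AE cannot be an SAE, whatever its seriousness.
- SAP 13 and 17.1.1: pre-dose AEs are held as medical history.

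**One event traced through.** Suppose a participant is hospitalized with a complication of the Screening endoscopy. The documents do not name this case. It is used because the Medical History sentence covers all medical occurrences without exception.
1. It begins after consent and before first dose, so 8.5.1 and Appendix 4 send it to Medical History.
2. Appendix 4 places that instruction among events that do not meet the AE definition.
3. Appendix 4 then says that such an event cannot be an SAE even if a seriousness criterion is met.
4. The 24-hour rule applies to SAEs, so on this path it is not reached.
5. On the other path (first sentence of 8.5.1, the 24-hour paragraph and 5.4) the same event is an SAE reportable within 24 hours.

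Both paths use current protocol text. Protocol 8.5 sends the reader to Appendix 4 for the definitions, and the 24-hour rule refers there too, so a careful site has good reason to take the path that ends in Medical History.

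One section sometimes set against the Medical History rule does not belong in the comparison. The duty in 8.5 to follow up procedure-related AEs is compatible with that rule, because it can refer to the Week 13 and Early Termination endoscopies.

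**The case against.** The best defence is that the disputed sentence only chooses an eCRF page. In 8.5.1 it does not mention SAEs, and the 24-hour rule that follows has no first-dose limit. In Appendix 4 it is the tail of a bullet about abnormal findings from the underlying disease. The examples attached to the rule that a non-AE cannot be an SAE concern hospitalization or death from the disease under study, not procedural harm. SAE reports go through an electronic collection tool with a paper form as back-up, and nothing shows that a Medical History entry blocks that route. Much of the text favours SAE capture from consent.

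This has weight. A reader might infer that the 24-hour route is definitely closed before first dose. The documents do not support that; it is one of two readings. But the defence does not remove the ambiguity: the sentence stands under a heading for non-AEs, has no exception for serious or procedural events, and is followed by an express bar on SAE status.

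A reader might also infer that the SAP's worsening rule cannot be applied to Screening-onset conditions because no baseline grade exists. That goes too far. Appendix 4 counts exacerbation of a chronic or intermittent preexisting condition as an AE in its own right, so worsening on drug can be entered as a new post-dose AE. The eCRF is not among the documents, so whether Medical History carries a grade or seriousness field is unknown.

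Finally, holding ordinary non-serious pre-dose events as medical history is a choice that the protocol and SAP share, and it can stay.

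**Conclusion.** The contradiction is real and should be corrected. It lies within 8.5.1 itself and between Appendix 4 on one side and 5.4, the Schedule of Activities, 6.10 and SAP 17.1.1 on the other. On the Appendix 4 reading, a serious complication of a mandatory study procedure could go unreported within 24 hours and not appear as an SAE.

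The exposure is every consented person from ICF signature to first dose: nominally up to 28 days, longer where Screening is extended under 8.1. That takes in the roughly 189 planned participants, all of whom need an endoscopy before randomization, plus the screen failures. No count of affected SAEs can be supported. The documents give neither the number screened nor a complication rate. A rate could not be applied to everyone screened in any case: 8.3.1.1 has rectal bleeding checked before the Screening endoscopy and 8.3.1.2 prefers endoscopy after other criteria are met, so some screen failures may never have one. Table 1 also accepts sigmoidoscopy at Screening.

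The consequence is for participant safety reporting and for the SAP's summary of serious pre-dose events. No efficacy result and no between-arm safety comparison depends on it. The conclusion rests on the protocol and SAP text alone; eCRF completion guidance, which was not available, may already steer sites correctly.

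**What to change.** - **Protocol Appendix 4:** remove the Medical History sentence from the list of events that do not meet the AE definition.
- **Protocol 8.5.1 and Appendix 4:** state that from ICF signature all SAEs and all study-procedure-related AEs are recorded on the AE/SAE page with a CTCAE grade, that the SAEs are reported within 24 hours, and that these events are flagged as not treatment-emergent. Other non-serious pre-dose events may remain in Medical History.
- **SAP 13 and 17.1.1:** take serious pre-dose AEs from the AE/SAE data. Where a Screening-onset condition is to be assessed for worsening, either use a recorded baseline grade or count the post-dose exacerbation as a new AE, and say which.

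The cost is a wording change in both documents, a matching line in the eCRF completion guidance, and slightly more AE entry at Screening. No visits or tests are added.
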